7.7 Week 47 Visit

The following procedures will be performed at the Week 23 visit:

- Measure vital signs including weight
- Perform ECG
- Perform neurological exam
- Perform physical exam
- Collect blood and urine for safety labs
- Administer ALSFRS-R questionnaire
- Perform Pulmonary Function Tests
- Columbia Suicide Severity Rating Scale (C-SSRS) – Since last visit
- Review and document concomitant medications and therapies
- Assess and document AEs
- Check study drug compliance
- Perform study drug accountability and collect all unused study drug, empty containers and nebulizers

7.8 Week 28 or 52 Phone Interview

The following procedures will be performed at the Week 28 Phone Call:

- Administer ALSFRS-R questionnaire
- Review and document concomitant medications and therapies
- Assess and document AEs

7.9 Final Safety Visit

Subjects who withdraw consent will be asked to come in for a Final Safety Visit as soon as possible, and will be asked to have a final Follow-Up Telephone Call (+ 5 days, but no earlier than 28 days, after subject's last dose of study drug) to assess for adverse events.

The following will be performed at the Final Safety Visit:

- Measure vital signs
- Perform ECG
- Perform neurological exam
- Perform physical exam
- Collect blood samples for safety labs
- Collect blood for biomarkers
- Administer ALSFRS-R questionnaire
- Perform U. Penn upper motor Neuron Burden (UMNB)
- Perform Pulmonary Function Tests
- Measure strength (ATLIS)
- Columbia Suicide Severity Rating Scale (C-SSRS) – Since last visit
- Review and document concomitant medications and therapies
- Assess and document AEs
- Check study drug compliance
- Perform study drug accountability and collect all unused study drug and empty containers and nebulizers

7.10 Follow-up

After the Week 28 Follow-up Telephone Interview, subjects may be contacted every three months for up to two years, or until consent is withdrawn, in order to obtain vital status and clinical information including the ALSFRS-R. Additionally, two years of post-study access to subjects' medical records will be requested to allow for review in combination with study data in order to investigate any correlation between imaging data collected during this study and subjects' clinical outcomes.

8 CLINICAL ASSESSMENTS AND OUTCOME MEASURES

8.1 Clinical Variables

Assessments will be performed at designated time-points throughout the study for clinical evaluation. In addition to the assessments evaluated below, subjects will provide information on their demographics, past medical history, including ALS, as well as concomitant medication usage.

8.1.1 Vital Signs, Height & Weight

Vital signs, including systolic and diastolic blood pressure, pulse rate (radial artery)/minute, respiratory rate/minute, temperature and weight will be assessed at specified visits. Height will be measured and recorded at the Screening Visit only.

8.1.2 Clinical Laboratory Assessments

The following safety laboratory tests will be performed during the study:

- Hematology with differential panel and urinalysis: complete blood count with differential (hematocrit, hemoglobin, platelet count, RBC indices, Total RBC, Total WBC, and WBC & differential)
- Blood chemistry panel/Liver function tests (LFTs): alanine aminotransferase (ALT (SGPT)), aspartate aminotransferase (AST (SGOT)), albumin, alkaline phosphatase, bicarbonate, blood urea nitrogen, calcium, chloride, creatinine, glucose, magnesium, phosphate, potassium, sodium, total bilirubin and total protein
- Urine human chorionic gonadotrophin (hCG) for women of childbearing potential (WOCBP) STAT quantitative serum hCG testing will also be performed prior to the MRI/PET scan for all WOCBP.

Additional testing may be ordered if needed, to further assess an AE, or if there is any suspicion that a subject may be pregnant, throughout the course of the study.

8.1.3 Physical Examination

A physical examination will be performed and recorded. The following systems will be examined: head/neck, eyes, ears, nose/throat, cardiovascular, lungs, abdomen, musculoskeletal, central nervous system, extremities, and skin.

8.1.4 Neurological Examination

A neurological examination will be performed and recorded.

8.1.5 Adverse Events

AEs will be documented at each study visit, including the final telephone call 28 days after the last dose of study drug. Information on adverse effects of study medication and on inter-current events will be determined at each visit by direct questioning of the subjects and review of concomitant medications.

8.1.6 ALSFRS-R

The ALSFRS-R is a quickly administered (5 minutes) ordinal rating scale (ratings 0 to 4) used to determine subjects' assessment of their capability and independence in 12 functional activities. All 12 activities are relevant in ALS. Initial validity was established by documenting that in ALS patients, change in ALSFRS-R scores correlated with change in strength over time, was closely associated with quality of life measures, and predicted survival. The test-retest reliability is greater than 0.88 for all test items. The advantages of the ALSFRS-R are that the categories are relevant to ALS, it is a sensitive and reliable tool for assessing activities of daily living function in those with ALS, and it is quickly administered. With appropriate training the ALSFRS-R can be administered with high inter-rater reliability and test-retest reliability. The ALSFRS-R can be administered by phone with good inter-rater and test-retest reliability. The equivalency of phone versus in-person testing, and the equivalency of study subject versus caregiver responses have also recently been established. Therefore, if necessary, the ALSFRS-R may be given to the study subject over the phone.

8.1.7 Pulmonary Function Testing

Pulmonary Function Testing includes Slow Vital Capacity (SVC).

Slow Vital Capacity (SVC): The vital capacity (VC) (percent of predicted normal) will be determined, using the upright slow VC method. The VC can be measured using conventional spirometers that have had a calibration check prior to subject testing. A printout from the spirometer of all VC trials will be retained. Three VC trials are required for each testing session, however up to 5 trials may be performed if the variability between the highest and second highest VC is 10% or greater for the first 3 trials. Only the 3 best trials are recorded on the CRF.

8.1.8 C-SSRS

The US FDA recommends the use of a suicidality assessment instrument that maps to the Columbia Classification Algorithm for Suicide Assessment (C-CASA)⁶². The C-CASA was developed to assist the FDA in coding suicidality data accumulated during the conduct of clinical

trials of antidepressant drugs. One such assessment instrument is the Columbia Suicide Severity Rating Scale (C-SSRS)⁶³. The C-SSRS involves a series of probing questions to inquire about possible suicidal thinking and behavior.

Only investigators who have been fully trained in the administration of the C-SSRS will assess subject suicidality. As part of training, investigators are prepared to respond to and manage instances in which patients express suicidal ideation or exhibit suicidal behavior.

At the Baseline Visit, the C-SSRS *Baseline* version will be administered. This version is used to assess suicidality over the subject's lifetime and specifically for the previous 6 month time period.

At the Week 11, Week 23, Week 35, Week 47, and the Final Safety visit, as applicable, the *Since Last Visit* version of the C-SSRS will be administered. This version of the scale assesses suicidality since the subject's last visit.

Information obtained from: <http://www.cssrs.columbia.edu/>

8.1.9 Upper Motor Neuron-Burden (UMN-B)

The Penn Upper Motor Neuron-Burden (UMN-B) is the total number of pathological UMN signs on examination including pathologically brisk biceps, supinator, triceps, finger, knee and ankle reflexes, and extensor plantar responses assessed bilaterally and brisk facial and jaw jerks (9). The scale is a combination of Ashworth, Reflexes, and Pseudobulbar Affect scale (Range score: 0 to 32).

The UMN also includes scoring of the Center for Neurologic Study-Lability Scale (CNS-LS), a 7-item self report scale that assesses pseudobulbar affect (PBA) by measuring the perceived frequency of PBA episodes (laughing or crying) and the Ashworth Spasticity Scale, a standard measure for spasticity that has been used in numerous ALS clinical trials to assess spasticity due to upper motor neuron dysfunction in ALS. Data is generated from the clinical exam and scored from 1 to 5, the lowest score indicating normal tone and the highest extreme spasticity.

8.1.10 Blood Biomarkers

Subjects will also be asked to provide blood samples for biomarker analysis per Schedule of Activities. These blood samples will be stored in a sample repository. These samples will be used for biomarker research. All samples will be labeled with a code. The code will not include any identifiable information. Any analysis performed on these samples is for research purposes only.

Unused samples will remain in the biorepository for future ALS-related research. There is no scheduled date on which the samples will be destroyed. Samples may be stored for research until they are used, damaged, decayed or otherwise unfit for analysis. Subjects have the option of declining participation in this portion of the study at any time by withdrawing their consent to have their sample used. However, it will not be possible to destroy samples that may have already been used.

8.1.11 Strength measurement (ATLIS)

Changes in strength will be measured using ATLIS (Accurate Test of Limb Isometric Strength), a non-invasive device that allows measurements of isometric strength in 12 muscle groups of the arms and legs using a standard protocol (elbow and knee flexion and extension, grip, and dorsiflexion). ATLIS consists of a frame with metal uprights. A wireless load cell is attached to adjustable testing stations positioned on the frame. The load cell transmits data (peak force) to a laptop computer using wireless technology. The General Hospital Corporation was granted a patent for this device by the US Patent Office (Patent # 7,493,812 issued 2/24/09). This device is not FDA approved.

8.1.12 Neuroimaging

Subjects in the Imaging group will undergo Magnetic Resonance Imaging (MRI) / Positron Emission Tomography (PET) twice during the course of the study. MR-PET scanning will be performed simultaneously using the Siemens 3 Tesla TIM Trio whole-body MRI system with a head PET camera insert. The goal of these scans is to measure activated microglia in study participants before treatment and after several weeks of treatment. The first scan will occur between the Screening and the Baseline visits (*off* treatment), after subject eligibility has been confirmed by TSPO affinity binding assay. The second scan will occur between the Week 18 and Week 23 visits (*on* treatment). Neuroimaging will be performed at the MGH Martinos Center for Biomedical Imaging. Subjects will be asked to lie still in a supine position for the duration of the study, which will take approximately 90 min.

9 SAFETY AND ADVERSE EVENTS

The AE definitions and reporting procedures provided in this protocol comply with all applicable regulations and ICH guidelines. The PIs will carefully monitor each subject throughout the study for possible AEs. All AEs will be documented on CRFs designed specifically for this purpose. It is also important to report all AEs, especially those that result in permanent discontinuation of the investigational product being studied, whether serious or non-serious.

9.1 Definitions of AEs, Suspected Adverse Drug Reactions & SAEs

9.1.1 Adverse Event and Suspected Adverse Drug Reactions

An adverse event (AE) is any unfavorable and unintended sign (including a clinically significant abnormal laboratory finding, for example), symptom, or disease temporally associated with the study, use of a drug product or device whether or not considered related to the drug product or device.

Adverse drug reactions (ADR) are all noxious and unintended responses to a medicinal product related to any dose. The phrase “responses to a medicinal product” means that a causal relationship between a medicinal product and an adverse event is at least a reasonable possibility, i.e., the relationship cannot be ruled out. Therefore, a subset of AEs can be classified as suspected ADRs, if there is a causal relationship to the medicinal product.

Examples of AEs include: new conditions, worsening of pre-existing conditions, clinically significant abnormal physical examination signs (i.e. skin rash, peripheral edema, etc), or clinically significant abnormal test results (i.e. lab values or vital signs), with the exception of outcome measure results, which are not being recorded as AEs in this trial (they are being collected, but analyzed separately). Stable chronic conditions (i.e., diabetes, arthritis) that are present prior to the start of the study and do not worsen during the trial are NOT considered AEs. Chronic conditions that occur more frequently (for intermittent conditions) or with greater severity, would be considered as worsened and therefore would be recorded as AEs.

AEs are generally detected in two ways:

Clinical → symptoms reported by the subject or signs detected on examination.

Ancillary Tests → abnormalities of vital signs, laboratory tests, and other diagnostic procedures (other than the outcome measures, the results of which are not being captured as AEs).

For the purposes of this study, symptoms of progression/worsening of ALS, including ‘normal’ progression, will be recorded as AEs.

The following measures of disease progression will not be recorded as AEs even if they worsen (they are being recorded and analyzed separately): vital capacity results and ALSFRS-R results.

If discernible at the time of completing the AE log, a specific disease or syndrome rather than individual associated signs and symptoms should be identified by the PI and recorded on the AE log. However, if an observed or reported sign, symptom, or clinically significant laboratory anomaly is not considered by the Site Investigator to be a component of a specific disease or syndrome, then it should be recorded as a separate AE on the AE log. Clinically significant laboratory abnormalities, such as those that require intervention, are those that are identified as such by the PI.

Subjects will be monitored for AEs from the time they sign consent until completion of their participation in the study (defined as death, consent withdrawal, loss to follow up, early study termination for other reasons or following completion of the entire study).

9.1.2 Serious Adverse Events

A serious adverse event (SAE) is defined as an adverse event that meets any of the following criteria:

1. Results in death.
2. Is life threatening: that is, poses an immediate risk of death as the event occurred.
 - a. This serious criterion applies if the study subject, in the view of the PI or Sponsor, is at immediate risk of death from the AE as it occurs. It does not apply if an AE hypothetically might have caused death if it were more severe.
3. Requires inpatient hospitalization or prolongation of existing hospitalization.
 - a. Hospitalization for an elective procedure (including elective PEG tube/g-tube/feeding tube placement) or a routinely scheduled treatment is not an SAE by this criterion because an elective or scheduled “procedure” or a “treatment” is not an untoward medical occurrence.
4. Results in persistent or significant disability or incapacity.
 - a. This serious criterion applies if the “disability” caused by the reported AE results in a substantial disruption of the subject’s ability to carry out normal life functions.
5. Results in congenital anomaly or birth defect in the offspring of the subject (whether the subject is male or female).

6. Necessitates medical or surgical intervention to preclude permanent impairment of a body function or permanent damage to a body structure.
7. Important medical events that may not result in death, are not life-threatening, or do not require hospitalization may also be considered SAEs when, based upon appropriate medical judgment, they may jeopardize the subject and may require medical or surgical intervention to prevent one of the outcomes listed in this definition. Examples of such medical events include blood dyscrasias or convulsions that do not result in inpatient hospitalization, or the development of drug dependency or drug abuse.

An inpatient hospital admission in the absence of a precipitating, treatment-emergent, clinical AE may meet criteria for "seriousness" but is not an adverse experience, and will therefore, not be considered an SAE. An example of this would include a social admission (subject admitted for other reasons than medical, e.g., lives far from the hospital, has no place to sleep).

The PI is responsible for classifying AEs as serious or non-serious.

9.2 Assessment and Recording of Adverse Events

The PIs will carefully monitor each subject throughout the study for possible AEs. All AEs will be documented on CRFs designed specifically for this purpose. All AEs will be collected and reported in the electronic data capture (EDC) system. The PIs shall promptly review all information relevant to the safety of the investigational product, including all SAEs. Special attention will be paid to those that result in permanent discontinuation of the investigational product being studied, whether serious or non-serious.

9.2.1 Assessment of Adverse Events

At each visit (including telephone interviews), the subject will be asked if they have had any problems or symptoms since their last visit in order to determine the occurrence of AEs. If the subject reports an AE, the Investigator will probe further to determine:

1. Type of event
2. Date of onset and resolution (duration)
3. Severity (mild, moderate, severe)
4. Seriousness (does the event meet the above definition for an SAE)
5. Causality, relation to investigational product and disease
6. Action taken regarding investigational product
7. Outcome

9.2.2 Relatedness of Adverse Event to Investigational Product

The relationship of the AE to the investigational product should be specified by the PIs, using the following definitions:

RNS60 in ALS

V 4.0

1/29/2016

1. Not Related: Concomitant illness, accident or event with no reasonable association with treatment.
2. Unlikely: The reaction has little or no temporal sequence from administration of the investigational product, and/or a more likely alternative etiology exists.
3. Possibly Related: The reaction follows a reasonably temporal sequence from administration of the investigational product and follows a known response pattern to the suspected investigational product; the reaction could have been produced by the investigational product or could have been produced by the subject's clinical state or by other modes of therapy administered to the subject. (Suspected ADR)
4. Probably Related: The reaction follows a reasonably temporal sequence from administration of investigational product; is confirmed by discontinuation of the investigational product or by re-challenge; and cannot be reasonably explained by the known characteristics of the subject's clinical state. (Suspected ADR)
5. Definitely Related: The reaction follows a reasonable temporal sequence from administration of investigational product; that follows a known or expected response pattern to the investigational product; and that is confirmed by improvement on stopping or reducing the dosage of the investigational product, and reappearance of the reaction on repeated exposure. (Suspected ADR)

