9.2.3 Recording of Adverse Events

All clinical adverse events are recorded in the Adverse Event (AE) Log in the subject's study binder. Study staff should fill out the AE Log and enter the AE information into the EDC system within 48 hours of the site learning of a new AE or receiving an update on an existing AE.

Entries on the AE Log (and into the EDC) will include the following: name and severity of the event, the date of onset, the date of resolution, relationship to investigational product, action taken, and primary outcome of event.

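### The Possibly Related category in 9.2.2 demands a known response pattern, so a new type of reaction that 9.1.1 counts as a suspected ADR can fit none of the five ratings

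*Combined protocol and SAP*

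**What the plan says.** Section 9.1.1 sets the threshold for an ADR: "a causal relationship between a medicinal product and an adverse event is at least a reasonable possibility, i.e., the relationship cannot be ruled out". It does not ask whether the type of event has been seen before with the product.

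Section 9.2.2 governs the rating. Relatedness "should be specified by the PIs, using the following definitions", and five definitions follow. The last three are labelled as suspected ADRs.

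- **Not Related**: no reasonable association with treatment.
- **Unlikely**: little or no temporal relation, "and/or a more likely alternative etiology exists".
- **Possibly Related**: reasonable timing, and the event "follows a known response pattern to the suspected investigational product". The definition adds that either the product or something else could have produced the reaction.
- **Probably Related**: reasonable timing, the event "is confirmed by discontinuation of the investigational product or by re-challenge", and the subject's clinical state does not reasonably explain it.
- **Definitely Related**: reasonable timing, a reaction "that follows a known or expected response pattern to the investigational product", improvement on stopping or reducing the drug, and reappearance on repeated exposure.

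Item 5 of section 9.2.1 has the investigator determine "Causality, relation to investigational product and disease". Section 9.2.3 lists among the AE Log and EDC entries "relationship to investigational product, action taken, and primary outcome of event". The visible text has no unassessable category and no default rating.

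**The concern.** The two sections apply different tests to the same label. Under 9.1.1, suspicion needs only that causation is a live possibility. Under 9.2.2, the entry-level suspected-ADR category also needs prior knowledge of the reaction, which a new type of reaction lacks by definition.

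Because the log requires a rating, the PI facing such an event has two choices. One is to rate it below suspected ADR, which conflicts with 9.1.1. The other is to use Possibly Related against its own wording. Two investigators could reasonably differ, and only one of the two codings would carry the suspected-ADR label.

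This is a single-centre, open-label pilot of 18 people with safety as a primary outcome. Unfamiliar reactions are what such a study most needs to flag.

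**Working it through.** The plan states no figure on this point, so the check is a logical one: write each definition as a rule and see which events satisfy none.

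**Criteria, all from 9.2.2.** T = reasonable timing; M = a more likely alternative cause; K = known response pattern; D = improvement on stopping or reducing; R = reappearance on re-exposure; S = clinical state could reasonably explain the event. The event is taken to have a reasonable association with the drug, so that 9.1.1 applies.

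**Rules as written.**

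1. Not Related: no reasonable association (excluded by the premise).
2. Unlikely: not T, or M.
3. Possibly: T and K.
4. Probably: T and (D or R) and not S.
5. Definitely: T and K and D and R.

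The further clause in Possibly Related, that the drug or something else could have caused the event, is left out of rule 3. Adding it as another condition could only narrow the category.

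**The clear case.** Timing plausible, no likelier cause, new pattern, no confirmation: T = 1, M = 0, K = 0, D = 0, R = 0.

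- Rule 1 fails: there is a reasonable association.
- Rule 2 fails: timing is good and no alternative is likelier.
- Rule 3 fails: K = 0.
- Rule 4 fails: neither D nor R.
- Rule 5 fails: K = 0, D = 0 and R = 0.

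Categories met: 0 of 5. Set K = 1 and rule 3 alone is met: 1 of 5.

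**Full enumeration for a new-pattern event (K = 0).** T, M, D, R and S give 2^5 = 32 combinations.

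| Combinations | Count | Category |
|---|---|---|
| T = 0 | 16 | Unlikely |
| T = 1, M = 1 | 8 | Unlikely (some also Probably) |
| T = 1, M = 0, D or R, S = 0 | 3 | Probably |
| T = 1, M = 0, no D, no R | 2 | none |
| T = 1, M = 0, D or R, S = 1 | 3 | none |

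The total is 16 + 8 + 3 + 2 + 3 = 32, of which 2 + 3 = 5 have no category. With K = 1 the number without a category is 0 of 32, because every event with T = 1 meets rule 3 and every event with T = 0 meets rule 2.

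There are therefore two routes into the gap. In the first, nothing confirms the event, for example because it happened once or the drug was continued. In the second, stopping or re-challenge does confirm it, but the clinical state could also explain it. The second route matters in ALS, where 9.1.1 has symptoms of disease progression recorded as AEs.

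**After deleting the pattern condition.** Rule 3 becomes T alone. The clear case then meets rule 3 only (1 of 5), and 0 of 32 combinations are left over. A new-pattern event with a likelier alternative and no confirmation meets rule 2 only as written; after the edit it meets rules 2 and 3, so an order of precedence is needed.

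The 32 combinations are not equally likely. 5 of 32 describes the coverage of the definitions and is not a rate of affected events.

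**The case against.** **The scale is a guide to clinical judgement, and its intent is clear.** Possibly Related goes on to say that the product or something else could have caused the reaction, which is close to the 9.1.1 test. A sensible PI may well use it for a new reaction. This stands as evidence of intent. It does not remove a condition joined by *and*, and it does not stop another PI from choosing Unlikely.

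**The wording is permissive.** Section 9.1.1 says AEs can be classified as suspected ADRs, and 9.2.2 says relatedness should be specified. This softens the conflict but supplies no rating for the uncovered event.

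**A one-off event under daily dosing is weak evidence of causation.** Non-recurrence on continued drug is in effect a negative re-challenge, so a low rating may lose little. This stands for that kind of event. It does not cover an event that persists on drug, or one that is confirmed on stopping but could also be explained by the disease.

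**No visible decision depends on the gap.** AEs are captured whatever their rating. The safety outcome in 3.2 and the stopping provision in 10.1 do not use relatedness. Section 10.1 sends unanticipated problems to the ethics committee without tying this to the rating. Section 6.3 lets the PIs reduce or stop drug for related AEs or for other reasons, and its mandatory permanent discontinuation applies to serious or life-threatening events judged definitely related, a category the edit leaves alone. All of this stands and limits the consequence to coding.

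**The pattern clause does useful filtering.** With daily dosing, timing is nearly always plausible, so removing the clause loosens the category. This is a real cost and is addressed in the fix.

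**Conclusion.** The concern holds. As written, 9.2.2 contradicts the threshold in 9.1.1. A new type of reaction with plausible timing and no likelier cause fits none of the five definitions unless it is confirmed by stopping or re-challenge and the clinical state cannot explain it. Of the 3 suspected-ADR categories, 2 require a known or expected pattern and the third requires confirmation.

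The conclusion rests on reading *and* in Possibly Related as joining two required conditions, and on there being no default rule, since none is visible. Redacted background might list known effects of the product, but no such list would make a new reaction a known one.

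The effect is a missing or inconsistent code in a required AE Log and EDC field. Its frequency cannot be estimated from the documents. The change should be made because it removes a direct conflict between two safety definitions, not because the trial's main safety results are at risk.

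**What to change.** In category 3 of 9.2.2, delete the requirement that the event "follows a known response pattern to the suspected investigational product". What remains, plausible timing and a reaction that the drug or something else could have produced, agrees with 9.1.1. Add one sentence saying that an event with a more likely alternative cause is rated Unlikely even when its timing is plausible. Category 5 stays unchanged, and with it the mandatory discontinuation rule in 6.3.

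The cost is one clause removed and one sentence added, with no new visit, assessment or sample size change. The drawback is that more events will be rated as suspected ADRs. Drug is scheduled on 1 infusion day plus 6 inhalation days, which is 7 days in 7 (24 × 7 = 168 scheduled dosing days in the core study), so timing will screen out little. The alternative-cause test in category 2 becomes the main filter, and the PIs should apply it deliberately.
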